6.4. Description of the clinical procedures and methods relating to the clinical investigation

Recruitment of healthy subjects is done through local advertising. Recruitment of patient-subjects with eye disease is done at the clinic Sundets Öganläkare.

Coordinated registration and allocation of participant trial numbers will be required to enroll all participants (see section 6.3). The Principal Investigator ensures through the Informed Consent Form that the trial objective, process and all trial subject rights are clear to the subject.

All participants (healthy subjects and patient-subjects) are considered to be enrolled into the clinical trial following the informed consent is signed, the evaluation of the medical history and the inclusion criteria, confirmation of eligibility, completion of the registration, allocation of the participant trial number and the investigation performance phase.

The overall purpose is to investigate if the investigational device can produce clear hyperspectral imaging of retinal changes by detecting structures and conditions in the retina and to compare the hyperspectral imaging with the expert diagnosis, as well as to investigate if additional signs of reduced oxygenation can be seen in retinal disease.

The admission visit (visit 1) is carried out as planned with visual acuity, refraction, pressure, field of view (if applicable), OCT and corneal microscope examination. Records of age and sex, other diseases and treatment are obtained. The subject will be administered pupil dilating drops of tropicamide 1% and phenylephrine hydrochloride 10% are instilled in each eye at the time of the examination. Images of the retina of the subject will be taken with the use of the Mantis Photonics hyperspectral camera by the medical staff members at the investigational site. The subjects are usually sent home after the image is taken when there are no inconveniences for the subjects.

The overview of the clinical investigation provides a review of each visit describing clinical investigation-related procedure(s) the subject undergoes during each visit:

Procedure	Visit 1 - part 1	Visit 1 - part 2	Visit 1 - part 3
	Admission & screening phase	Application of the investigation device phase	End phase
Informed consent	x		
Inclusion/exclusion criteria	x		
Medical history review	x		
Eligibility	x		
Administration of eye drops and flashlight taking image		x	
Adverse Events review		x	x
Clinical investigation end			x

After the phases above, the retinal images are taken and analyzed. Researchers such as (Meinke 2007) have demonstrated how one can estimate the blood oxygenation at a given location (image pixel) based on the frequency absorbance spectrum. The reference frequency absorbance spectrum of fully oxygenated blood (100% oxygenation) and fully oxygen-depleted blood (0% oxygenation) are known and tabulated by comparing the pixel's frequency spectrum to the frequency absorbance spectrum of two reference curves allows us to estimate the oxygenation of the blood at the respective location.

We will compare oxygenation between arteries and veins. The largest artery and vein at the superior and the inferior temporal vascular tree will be marked for each eye. We will analyze 10 to 20 consecutive points from the papillary edge along the vascular tree to measure the mean vessel oxygenation level and the evolution of the oxygenation level. The initial image analysis can be followed by machine learning to distinguish between a normal retina and a retina affected by a disease (the ophthalmologist's diagnosis can be taken as ground truth).

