6.1. General information

This single centre, open, controlled investigation will be conducted at the clinic of Sundets Ögonläkare, Helsingborg (patients and healthy subjects).

In this study, patients with known retinal oxygenation problems and volunteers without known or suspected retinal pathologies will be subjected to retinal scanning. The trial's aim is not to demonstrate any treatment effect between the treatment group and the control group. Thus, no control group is defined. The study objective is the demonstration of the feasibility and applicability of the technique.

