For subjects enrolled, this number will consist of 01 for the first subject, 02 for the second subject and so on. This number will be the unique identifier of the subject (i.e. enrolment number) and written on each page of the paper/electronic Case Report Form booklet and all other documentation relating to that subject.

Each subject that is enrolled into the study will have their study participation recorded in their medical records, a copy of their signed and dated consent form and a patient information sheet should also be placed on his patient files to identify the subject as participating in a clinical investigation.

Investigation population

The investigation population are healthy persons and patients (120 subjects in total).

Approximately 100 male or female subjects, 18 years or older, with an ophthalmological disease, disorder, illness or problem will be recruited in this investigation.

Approximately 20 healthy male or female subjects, 18 years or older, will be recruited in this investigation.

The investigation population is not a *vulnerable population* as described by GCP.

Criteria and procedures for subject withdrawal or discontinuation

Subjects are free to discontinue participation in the clinical investigation at any time, and without prejudice to further treatment. Subjects who discontinue the clinical investigation should always be asked about the reason(s) for their discontinuation and about the presence of any AE/ADE or DD and, if possible, be assessed by an investigator. AE/ADE should be followed up. Subjects will be informed clearly they have no obligation to give a reason for discontinuation or to answer other questions.

Subjects may be withdrawn from clinical investigation at any time, at the discretion of the investigator.

Incorrectly enrolled subjects will be withdrawn from further clinical investigation. A subject may, however, continue the investigation under special circumstances (i.e., if continuation of investigation or follow-up actions are necessary for the subject's safety and well-being, and the continuation of the investigation is not expected to be associated with any risk or discomfort for the subject).

When a subject redraws or is discontinued from the research, the subject recruitment continues until the defined number of both patient and healthy subjects are maintained in the study dataset.

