6.5. Timeline of the clinical investigation

The prefixed time schedule for the Investigation is as follows:

- August 2022: putting equipment in place.
- October-November2022: recruiting healthy subjects.
- December 2022-February 2023: analyse the data from healthy subjects.
- October-December 2022: recruiting patients with eye disease.
- January-March 2023: analysing all data.

- April 2023 - February 2024: compiling and evaluating results.
- March 2024- July 2024: writing, submitting and revising a scientific article.

The Sponsor and Principal Investigator will notify the Swedish Medical Products Agency (Läkemedelsverket) within 15 days after end of the clinical investigation and the Sponsor will send the clinical investigation report within 1 year after the end of the clinical investigation including an easily understandable summary.

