Appendix 1: Financial conditions

Parties agreed on the following responsibilities:

Mantis Photonics AB is responsible for designing, building, installing and maintaining the research prototype. The device will be moved to the main location of Sundets Ögonläkare by Mantis Photonics and installed in location. Mantis Photonics will not invoice any costs to the other parties for these actions and responsibilities.

As described in the CIP, the Subject is guided by Sundets Ögonläkare ophthalmologist [name]. The Subject will be introduced to and explained the informed consent document. After obtaining consent form to perform the retinal eye exam after being guided for the Subject, ophthalmologist [name] will perform the retinal scan with the research prototype provided by Mantis Photonics AB. Sundets Ögonläkare will invoice 50 SEK per patient for these actions and responsibilities additional to demonstratable costs such as patient transportation reimbursement and costs for communication and patient recruitment. [name] makes her time and expertise available to Mantis Photonics as part of her involvement with Mantis Photonics as a board member and shareholder.

Parties agree the listed compensations are fair and reasonable compensation.

1. The Parties declare that the agreement is in reasonable proportion to the services provided and have agreed no other financial compensation from the Sponsor other than the agreements referred to in this Agreement.
2. If any increase in compensation due for the conduct of the study is necessary or appropriate, the Parties shall negotiate further remuneration, and the Sponsor shall provide a written notice in the form of a budget increase letter. This includes an increase in the amount of Subjects to be enrolled, and if amendments are made to the CIP which result in increased cost for the Institution/Site.

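### Nothing in the plan masks whoever marks vessels or reads images, and the healthy eyes are analysed first as a known group against fixed oxygenation limits

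*Combined protocol and SAP*

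**What the plan says.** **Design.** Section 6.1 begins: "This single centre, open, controlled investigation will be conducted at the clinic of" a named eye clinic. Section 7.1 repeats that the study is open and plans descriptive statistics only.

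**Marking and measuring.** Section 6.4: "The largest artery and vein at the superior and the inferior temporal vascular tree will be marked for each eye". It continues: "We will analyze 10 to 20 consecutive points from the papillary edge along the vascular tree". It does not say who does this, what that person may know, or how the number of points is settled.

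**Reference diagnosis.** Section 6.4 plans a comparison of the hyperspectral images with expert diagnosis. For an optional machine-learning step it adds that "the ophthalmologist's diagnosis can be taken as ground truth".

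**Healthy limits.** Section 5.2 lists, for healthy retinas, arterial oxygenation above 95% and venous oxygenation below 70%.

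**Labels.** Sections 8.1 and 8.3 label images with the subject ID only. Section 6.3 issues the ID in enrolment order: "this number will consist of 01 for the first subject, 02 for the second subject and so on".

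**Order of work.** Section 6.5: "December 2022-February 2023: analyse the data from healthy subjects". Analysis of all data follows in January to March 2023.

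**Who scans.** Appendix 1 says the site ophthalmologist "will perform the retinal scan with the research prototype provided by Mantis Photonics AB" and gives time and expertise "as part of her involvement with Mantis Photonics as a board member and shareholder". Section 6.4 assigns image-taking to medical staff at the site, without naming a role.

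**The concern.** Placing a vessel path, judging where the disc edge lies, deciding how many points to average and rejecting a poor image all involve judgement. If the person doing this knows that the eye is healthy, and that healthy arteries should read above 95% and veins below 70%, the choices can lean that way without any intent. Such a lean is systematic, so it does not average out over 20 healthy subjects or 120 in total.

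Three results are exposed: the oxygenation limits in healthy eyes, the comparison of healthy with diseased eyes, and the comparison of the images with expert diagnosis. The artery-vein contrast within an eye is less exposed to knowledge of group, because the two vessel types can be told apart on the image in either group.

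A financial interest close to the measurements makes the missing separation of roles harder to defend when the results are published.

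**Working it through.** The plan states no figure for reader error or bias, so there is nothing to reproduce. The check has two parts.

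**1. Does the subject ID mask group?**

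- *Healthy subjects: no.* Section 6.5 analyses them as their own batch from December to February, so group is known from the batch itself, whatever the label.
- *Patients: probably not, but this is inference.* Healthy recruitment runs October to November 2022 and patient recruitment October to December 2022. The periods overlap and the numbers carry no group code, so October and November numbers may interleave. December numbers are patients if the timetable is kept. Someone who has already handled the healthy batch also knows by elimination that every remaining ID is a patient.
- *Other routes.* Section 6.3 puts the same ID on every CRF page, and the CRF documents the eligibility criteria. Nothing bars the marker from seeing it.

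**2. How much could the open point count matter?**

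This is an illustration only. The count of 10 to 20 comes from section 6.4. The point-to-point SD (5 or 10 percentage points) and the correlation r between neighbouring points (0, 0.5 or 0.8) are assumptions and appear nowhere in the documents.

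Let x_j be the deviation of point j from the true vessel mean, with x_j = r·x_(j−1) + √(1−r²)·e_j, scaled to the chosen SD. The vessel reading from k points is M_k = (x_1 + … + x_k)/k. With k fixed at 20, the expected error is 0. If the most favourable k is always chosen, the bias is E[max of M_10, …, M_20]. If artery and vein are each pushed in the helpful direction, the artery-vein difference is inflated by twice that. Means over 100,000 simulated vessels:

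| SD | r | Fixed 20 points | Best of 10 to 20 | Artery-vein difference |
|---|---|---|---|---|
| 5 | 0 | 0.00 | 0.70 | 1.40 |
| 5 | 0.5 | 0.01 | 0.94 | 1.89 |
| 5 | 0.8 | 0.00 | 1.02 | 2.05 |
| 10 | 0 | 0.00 | 1.41 | 2.82 |
| 10 | 0.5 | 0.02 | 1.87 | 3.75 |
| 10 | 0.8 | 0.00 | 2.05 | 4.10 |

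So the open count alone allows at most about 0.7 to 2.1 points per vessel mean under these assumptions, and a fixed count removes it. Choice of vessel, image or starting edge is not included.

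**The case against.** The strongest reply is that this is an open, descriptive pilot with no hypothesis test. Images carry only an ID, and the rule of largest vessel and consecutive points from the disc edge already limits choice. Much of this stands. No error rate is at stake, and the rule does narrow the room for judgement. The plan does not say that marking is done by hand; if it were automated, knowledge of group would matter less for the vessel readings. But in a descriptive study the readings are the result, and bias in a mean does not depend on there being a test.

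Four stronger readings are tempting and are not supported:

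- *That all images are marked and read with disease group in view.* This follows for the healthy batch only. For patients the plan is silent.
- *That the shareholder marks vessels, reads images or sets the reference diagnosis.* Appendix 1 documents scanning only, and section 6.4 does not say which ophthalmologist diagnoses. What stands is that no rule separates these roles.
- *That a shift of 1.7 to 4.2 points is to be expected.* That range comes from picking the best of 2 or 3 vessel paths with an assumed SD of 3 to 5 points (0.567 × 3 = 1.7; 0.848 × 5 = 4.2). It runs against the largest-vessel rule and assumes that the marker sees each reading before choosing.
- *That every outcome in section 5.2 rests on the vessel readings.* Detection of structures and optic nerve thinning, for example, does not.

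Masking would also be incomplete. Haemorrhages or deposits can show on the image itself. Under REQ-SW-5 in section 2.1 the operator checks scan quality on the spot and may act on it, and that decision cannot be masked.

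**Conclusion.** The concern holds in a limited form. The plan provides no masking for marking or reading, makes group known for the healthy batch, sets target values for that same batch, and leaves the number of points open. Nothing keeps the scanning ophthalmologist, who has a financial interest, from also marking or reading. This last point takes Appendix 1, where names are removed, to describe one person throughout.

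The size of any bias cannot be derived from the documents. The 0.7 to 2.1 points per vessel mean is a worst case from the open count alone, on assumed SDs and correlations, and is not a prediction. The point merits a change because the remedy is cheap and acts directly on the healthy limits and the healthy-disease comparison.

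**What to change.** Amend sections 6.4 and 6.5:

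1. Before marking, replace the subject IDs on image files with random codes and mark healthy and patient images in one mixed batch. Limit the December-February healthy-only work to technical checks.
2. Have vessels marked and images read without group, diagnosis or OCT, by someone already on the study team other than the scanning shareholder. Record the role in the delegation log of section 8.1.
3. Fix one number of points per vessel in advance.
4. Record the diagnosis in the CRF before the hyperspectral image is viewed, and decide rejections of stored images before decoding.
5. Reconcile section 6.4 with Appendix 1 on who takes the images.

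**Cost.** A recoding step and revised wording, with no added procedure for subjects. The marking load is unchanged: if both eyes are imaged, 120 subjects × 2 eyes × 4 vessels = 960 vessels. The plan names no analyst, so if nobody suitable is on the team, another person is needed. Healthy-only performance results move from the December-February window to the January-March one. Because marking uses stored images, it can still be done masked after acquisition. Disease visible on the image and retakes during the visit remain unmasked and should be reported as limitations.

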6.5. Timeline of the clinical investigation

The prefixed time schedule for the Investigation is as follows:

- August 2022: putting equipment in place.
- October-November2022: recruiting healthy subjects.
- December 2022-February 2023: analyse the data from healthy subjects.
- October-December 2022: recruiting patients with eye disease.
- January-March 2023: analysing all data.

- April 2023 - February 2024: compiling and evaluating results.
- March 2024- July 2024: writing, submitting and revising a scientific article.

The Sponsor and Principal Investigator will notify the Swedish Medical Products Agency (Läkemedelsverket) within 15 days after end of the clinical investigation and the Sponsor will send the clinical investigation report within 1 year after the end of the clinical investigation including an easily understandable summary.

6.6. Monitoring plan

The clinical investigation will be monitored by a Sponsor representative before the clinical investigation begins, during the clinical investigation conduct, and after the clinical investigation has been completed, so as to ensure that the clinical investigation is carried out according to the CIP, the relevant laws and regulations and the rules of Good Clinical Practice (GCP) and that data is collected, documented, and reported according to EN-ISO 14155:2020 and applicable ethical and regulatory requirements. The document LU_LR_56_A Trial Monitoring Plan describes this.

The Sponsor will schedule the monitoring visits with advance notice and confirm the scheduling of the visit with the investigation site. The Sponsor representative should meet with the Principal Investigator at each monitoring visit.

The Principal Investigator and its representative staff members and the institution site will permit investigation-related monitoring, audits, and regulatory inspection(s), providing direct access to source data/documents to the Monitor. The subjects are informed of this during the informed consent discussion. The Monitor will sign a confidentiality agreement before receiving access to the medical records of the study subjects.

The monitoring is intended to ensure that the subject's rights, safety, and well-being are met as well as data in the CRF are complete, correct, and consistent with the source data.

At the conclusion of the monitoring visit, the Sponsor representative shall write a monitoring report detailing the activities performed during the visit with recommendations for action items and study site action. A follow-up letter to the study site detailing these recommendations and actions will be sent to the Principal Investigator.

The monitoring is intended to ensure that the subject's rights, safety, and well-being are met as well as data in the CRF are complete, correct, and consistent with the source data.

7. Statistical Considerations

7.1. Presentation of the data

The results from this open, controlled clinical investigation will be presented with descriptive statistics. No hypothesis testing is planned for this investigation.

Data listings will be prepared for all data. Certain data will be collated into summary tables and figures. Those summary tables and figures will be integrated into investigation reports.

7.2. Population for analysis

Safety Population

The population for the assessment of safety will include all enrolled subjects who provide at least the investigation performance phase (visit 1 - part2).

PP population

The Per Protocol (PP) population will include all subjects without significant protocol violations. Subjects identified as protocol violators will be documented and agreed upon before declaration of clean-file.

Population size

An estimated 120 people will be recruited for the study:

- Approximately 100 male or female subjects, 18 years or older, with an ophthalmological disease, disorder, illness or problem will be recruited in this investigation.
- Approximately 20 healthy male or female subjects, 18 years or older, will be recruited in this investigation.

7.3. Baseline characteristics

All variables measured at baseline will be summarized for the PP population using appropriate summary statistics.

7.4. Performance and safety measurement

All endpoints will be summarized as above and by visit. The result from the CRF will be summarized appropriately for all evaluable subjects. The number of subjects reporting one or more adverse events during the course of the investigation will be summarized using frequency counts.

7.1 Determination of sample size - sample size calculation

This is a descriptive investigation and the number of subjects has been chosen to be able to find explorative trends.

8 Data management

The data management includes all activities related to data handling regarding:

- Set-up of CRF and database.
- If necessary, specification of online checks.
- Data entry / data editing.
- Export of data.
- Creation of post-entry checks and listings.
- Reconciliation of SAE, SADE, ADE and DD.
- Measures implemented to ensure confidentiality of the records and personal data of subjects.
- Measures implemented in case of data security breach.

All data will be registered, managed, and stored in a manner that enables correct reporting, interpretation, and verification.

Subjects who participate in the clinical investigation are coded with a specific clinical investigation identification number (i.e., subject ID). All subjects are registered in a subject identification list (subject enrolment and identification list) that connects the subject's name and personal number with a clinical investigation identification number.

8.1 Case Report Form

The handling of all data on the CRFs will be the responsibility of the Principal Investigator.

It will be the responsibility of the Principal Investigator to ensure the accuracy of all data entered in the CRFs. The delegation log will identify all those staff members with responsibilities for data collection and handling, including those who have access to the trial database.

The Principal Investigator will be responsible for timely data entry, accuracy and completeness of a CRF for each individual subject. The personal data recorded on all documents will be regarded as confidential.

The Principal Investigator must record the subject's participation in this clinical investigation in the subject's patient files. In addition, the Principal Investigator must keep a separate list of all subjects entered into the clinical investigation showing each subject's name, date of birth and assigned subject number (for identification purposes).

Photos are marked with the subject ID. The photos shall not contain any information that can reveal the identity of the subject.

The CRFs will not bear the subject's name or other personal identifiable data. The subject's initials, date of birth and trial identification number, will be used for identification.

The Principal Investigator will make the original CRF's available to the Sponsor's designated monitor at each visit. At the conclusion of the clinical investigation, completed CRF's will be signed by the Principal Investigator and the original CRF's will be left with the Principal Investigator.

